6.5.2. Background UC Therapy

New UC therapies may not be started between 2 weeks prior to the screening flexible sigmoidoscopy/colonoscopy and the PCP Week 36 visit. Subjects requiring introduction of new therapies to treat UC will be discontinued from IP as described in Section [7.1.5](#).

5-ASA

Subjects should remain on their stable UC background oral 5-ASA therapy from 2 weeks prior to screening flexible sigmoidoscopy/colonoscopy used to assess the baseline Mayo score through the duration of their time on study. Any changes in existing UC background therapies should be discussed with the Sponsor's Medical Monitor (or designee), if possible.

Systemic steroid tapering

Subjects receiving oral prednisone \leq 20 mg/day (or equivalent) or beclomethasone \leq 5 mg/day or budesonide or budesonide MMX of \leq 9 mg/day should remain on their stable dose from 2 weeks prior to screening flexible sigmoidoscopy/colonoscopy used to assess the baseline Mayo score through the PCP Week 12 visit. At the discretion of the Investigator, systemic steroids may be tapered after the PCP Week 12 visit as described below. For subjects who cannot tolerate systemic steroid taper without recurrence of clinical symptoms of either UC or steroid withdrawal, the systemic steroid dose may be increased (up to the baseline dose if required).

Prednisone (or equivalent) tapering

- Subjects receiving prednisone at a dose of $>$ 10 mg/day (or equivalent) should have their dose reduced at a rate of 5 mg per week until a 10 mg/day dose is achieved.
- Subjects receiving prednisone at a dose of 10 mg/day (or equivalent) either or when this dose is achieved by tapering during the OLE, are to have their dose reduced at a rate of 2.5 mg per week until discontinuation.

Beclomethasone or Budesonide tapering

- Subjects receiving beclomethasone should taper their dose of 5 mg every day to 5 mg every other day for 2 weeks then discontinue beclomethasone.
- Subjects receiving budesonide or budesonide MMX should taper their dose of 9 mg every day to 9 mg every other day for 2 weeks then discontinue budesonide or budesonide MMX.

6.6. Continued Access to Investigational Product After the End of the Study

No additional intervention is planned beyond the OLE EOT visit.

6.7. Treatment of Overdose

Any dose of IP greater than the prescribed daily dose within the same calendar day will be considered an overdose.

There is no specific treatment recommended to treat an overdose of IP and the subject should receive treatment directed towards any symptoms manifested.

In the event of an overdose, the Investigator should:

- Contact the Sponsor's Medical Monitor (or designee) as soon as possible.

- Closely monitor the subject for any AE/SAE and laboratory abnormalities.
- Document the quantity of the excess dose as well as the duration of the overdose in the electronic case report form (eCRF).

Decisions regarding dose interruptions will be made by the Investigator in consultation with the Sponsor's Medical Monitor (or designee) based on the clinical evaluation of the subject.

6.8. Concomitant Therapy

At least a 4-hour interval is required between taking IP tablets and mineral supplements, and antacids that contain polyvalent cations (eg, iron, aluminum, and zinc).

Results from in vitro studies indicate that a glucuronide metabolite of GB004, GBD242, may be an inhibitor of OCT2 and CYP2C8.

If sensitive clinical substrates of OCT2 (such as metformin or dalfampridine) are used concomitantly with GB004, refer to the prescribing information of the clinical substrate for assessing the benefit and risk of concomitant use. Initiation of sensitive clinical substrates of OCT2 is permitted only after discussion with the Sponsor's Medical Monitor (or designee) and consideration of alternatives.

Concomitant use of sensitive substrates of CYP2C8 (eg, repaglinide, rosiglitazone, pioglitazone, and loperamide) is prohibited in this study pending further evaluation of the potential for GBD242 to inhibit CYP2C8 activity clinically.

Any medication or vaccine (including over-the-counter [OTC] or prescription medicines, vitamins, and/or herbal supplements) that the subject is receiving at the time of enrollment or receives during the study must be recorded along with:

- Reason for use
- Dates of administration including start and end dates
- Dosage information including dose and frequency

The Sponsor's Medical Monitor (or designee) should be contacted if there are any questions regarding concomitant or prior therapy.

6.8.1. Prohibited Medications Prior to the Screening Visit and Throughout the Study

Please refer to [Appendix 6](#) for further details regarding prohibited medications.

7. DISCONTINUATION OF INVESTIGATIONAL PRODUCT AND SUBJECT WITHDRAWAL FROM STUDY

7.1. Discontinuation of Investigational Product, Subject Withdrawal from the Study and Stopping Rules

Discontinuation of IP

In some instances, it may be necessary for a subject to permanently discontinue IP.

PCP: Permanent discontinuation of IP does not mean withdrawal from the study, and the subject will be encouraged to remain in the study and continue to complete any remaining PCP study visits as per the SoA (Section 1.3.1 – PCP) if the subject is not enrolling in the OLE. A follow-up visit will be conducted approximately 4 weeks after last dose of IP. The reason for discontinuation of IP will be recorded in the eCRF.

OLE: Subjects who permanently discontinue IP during the OLE will be withdrawn from the study, complete the End of OLE/ET visit, and will be asked to return for a Follow-up visit approximately 4 weeks after their last dose of IP to assess safety.

Withdrawal from the Study

Subjects have the right to withdraw from the study at any time and for any reason without prejudice to their future medical care by the Investigator or at the institution. The reason for subject withdrawal from the study will be recorded in the eCRF. At the time of withdrawal from the PCP, an Early Withdrawal from Study visit should be conducted, as shown in the SoA (Section 1.3.1 – PCP) and from the OLE, the EOT visit should be conducted as shown in the SoA (Section 1.3.2 – OLE). See the SoA for data to be collected at the time of study withdrawal and follow-up and for any further evaluations that need to be completed. If a subject withdraws from the study, he/she may request destruction of any samples taken and not tested, and the Investigator must document this in the site study records.

A subject may discontinue IP or withdraw from the study for the following reasons:

- Adverse event
- Death
- Lack of efficacy
- Lost to follow-up
- Non-compliance with study drug
- Physician decision
- Pregnancy
- Protocol deviation
- Site terminated by Sponsor
- Study terminated by Sponsor

- Withdrawal by subject

For stopping criteria related to hemoglobin, nausea, and dizziness, refer to Section [7.1.1](#).

For stopping criteria relating to QTcF prolongation, refer to Section [7.1.2](#).

For liver chemistry abnormality actions and follow-up assessments, refer to Section [7.1.3](#) and [Appendix 7](#) and for dose modification, refer to Section [6.5.1](#).

Pregnancy is a criterion for mandatory permanent discontinuation of IP (see Section [7.1.4](#)).

For stopping criteria related to introduction of new therapy to treat UC between 2 weeks prior to the screening flexible sigmoidoscopy/colonoscopy and the PCP Week 36 visit, refer to Section [7.1.5](#).

7.1.1. Hemoglobin, Nausea, and Dizziness Stopping Criteria

Individual subjects will be permanently discontinued from IP for any of the following:

- Hemoglobin increase of > 4 g/dL from baseline and above ULN, and is assessed by the Investigator as a related AE.
- Nausea that prevents daily activity, requires outpatient IV hydration, and is assessed by the Investigator as a related AE.
- Dizziness that prevents daily activity, requires medical intervention, and is assessed by the Investigator as a related AE.

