2.3.2. Risk Assessments

As of May 27, 2020, a total of 117 subjects, comprising 94 healthy volunteers and 23 subjects with active UC, have received GB004. GB004 Powder for Oral Solution has been studied in healthy volunteers receiving single and multiple doses up to 240 mg daily for 8 days (AKB-4924-CI-1001 and AKB-4924-CI-1002) and in subjects with active UC receiving 120 mg daily for 28 days (GB004-1101). GB004 formulations (Powder for Oral Solution and tablets) have been studied in healthy volunteers receiving doses up to 240 mg daily for 7 days (GB004-1902). There are no identified risks of GB004. There are 2 potential risks of GB004.

These potential risks are:

- **Nausea:** The overall incidence of nausea was 18.8% (22/117) in GB004-treated subjects versus none in placebo-treated subjects. Nausea in GB004-treated subjects was generally characterized as: mild, occurring more frequently with GB004 doses of 120 mg or greater, first occurring within the first hour after the first dose and lasting 1 day, without concurrent vomiting, and of low clinical impact with infrequent discontinuations of GB004 (1 subject).
- **Dizziness:** The overall incidence of dizziness was 11.1% (13/117) in GB004-treated subjects versus 4.9% (2/41) in placebo-treated subjects. Dizziness in GB004-treated subjects was generally characterized as: mild, occurred more frequently with GB004 doses of 120 mg or greater, first occurring within 1 day after first dose and lasting 1 day, without impairment of function, and with no discontinuation of GB004.

Preliminary safety results from the study of GB004 tablet formulations (GB004-1902) show that nausea and dizziness were reported less frequently than were previously reported with the solution formulation. GB004 formulations have been studied in a Phase 1 study (GB004-1902) in healthy volunteers receiving daily doses of 120 mg solution or placebo, or up to 240 mg tablet,

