delayed-release tablet, or placebo for 7 days. Overall, TEAEs were reported by 9 of 32 (28%) subjects who received GB004 and 3 of 10 (30%) subjects who received placebo. All TEAEs were mild in severity. TEAEs reported in more than one subject in the GB004 group included nausea (9% GB004; none in placebo), headache (9% GB004; 10% placebo), diarrhea (6% GB004; 20% placebo), and liver function test elevation (6% GB004; none in placebo). Preliminary safety results from this study suggest that GB004 formulations of 120 mg solution and up to 240 mg tablet, and 240 mg DR tablet are generally well tolerated in healthy subjects.

GB004 Powder for Oral Solution has been studied in subjects with active UC receiving daily doses of 120 mg in a Phase 1b study (GB004-1101). The majority of adverse events (AEs) were reported as Common Terminology Criteria for Adverse Events (CTCAE) Grade 1 or 2 in severity and were considered not related. The most common ($\geq 10\%$) TEAEs reported in GB004-treated subjects included nausea (21.7% GB004; 0% placebo) and dysgeusia (13% GB004; 0% placebo). Preliminary results suggest that GB004 Powder for Oral Solution 120 mg daily is generally well tolerated in subjects with active UC.

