6.5. Dose Modification

6.5.1. Investigational Product

Dose modification, as described below, may be considered for treatment-related AEs and liver chemistry laboratory abnormalities.

Dose reduction will be prescribed in two steps (as detailed in the Study Reference Manuals):

- First reduction step: IP dose will be reduced by 2 tablets BID
- Second reduction step (only if either treatment-related AE or liver function abnormality persist for 7 days following initiation of first step of dose reduction): IP dose will be reduced further by 1 tablet BID

Treatment-related AEs (other than liver chemistry laboratory abnormalities described below):

Dose modification of IP may be undertaken only after consultation and approval from the Sponsor's Medical Monitor (or designee) for AEs assessed by the Investigator as treatment-related, such as tolerability related AEs. Subjects may be requested to attend an unscheduled visit after dose reduction (before potential re-administration of IP at a higher dose as described below), to collect blood samples for safety and PK, if possible.

Liver chemistry laboratory abnormality:

- Dose modification of IP may be undertaken only after consultation and approval from the Sponsor's Medical Monitor (or designee) for confirmed ALT or AST $\geq 3 \times$ ULN and $< 5 \times$ ULN meeting the criterion described in [Table 6](#) in [Appendix 7](#).
- For confirmed ALT or AST $\geq 3 \times$ ULN meeting criteria in [Table 7](#) in [Appendix 7](#), IP should be discontinued.

In both study periods, following dose reduction, IP may be re-administered at a higher dose in consultation with the Sponsor's Medical Monitor (or designee).

After consultation and approval from the Sponsor's Medical Monitor (or designee), subjects with a dose reduction during the PCP may enter the OLE at the reduced dose (reduced number of tablets as specified above) or at full dose (480 mg BID).

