8. STUDY ASSESSMENTS AND PROCEDURES

Study procedures and their timing are summarized in the SoA (Section [1.3.1](#) – PCP and Section [1.3.2](#) – OLE). Protocol waivers or exemptions are not allowed.

- Immediate safety concerns should be discussed with the Sponsor's Medical Monitor (or designee) immediately upon occurrence or awareness to determine if the subject should continue or discontinue IP.
- Adherence to the study design requirements, including those specified in the SoA, is essential and required for study conduct.
- All screening evaluations must be completed and reviewed to confirm that potential subjects meet all eligibility criteria. The Investigator will maintain a screening log to record details of all subjects screened and to confirm eligibility or record reasons for screening failure, as applicable.
- In case of natural disasters or pandemics, some visits/study procedures may be done via virtual visits or at home visits. Refer to [Appendix 9](#) and Study Reference Manuals for more details.

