- Medical or surgical procedure (eg, endoscopy, appendectomy): the condition that leads to the procedure is the AE.
- Situations in which an untoward medical occurrence did not occur (social and/or convenience admission to a hospital).
- Anticipated day-to-day fluctuations of pre-existing disease(s) or condition(s) present or detected at the start of the study that do not worsen.
- Fluctuations in UC disease activity that do not worsen compared to a subject's medical history of UC

Definition of SAE

If an event is not an AE per definition above, then it cannot be an SAE even if serious conditions are met (eg, hospitalization for signs/symptoms of the disease under study, death due to progression of disease).

An SAE is defined as any untoward medical occurrence that, at any dose:**Results in death****Is life-threatening**

The term 'life-threatening' in the definition of 'serious' refers to an event in which the subject was at risk of death at the time of the event. It does not refer to an event, which hypothetically might have caused death, if it were more severe.

Requires inpatient hospitalization or prolongation of existing hospitalization

In general, hospitalization signifies that the subject has been detained (usually involving at least an overnight stay) at the hospital or emergency ward for observation and/or treatment that would not have been appropriate in the physician's office or outpatient setting. Complications that occur during hospitalization are AEs. If a complication prolongs hospitalization or fulfills any other serious criteria, the event is serious. When in doubt as to whether "hospitalization" occurred or was necessary, the AE should be considered serious.

Hospitalization for elective treatment of a pre-existing condition that did not worsen from baseline is not considered an AE.

Results in persistent disability/incapacity

- The term disability means a substantial disruption of a person's ability to conduct normal life functions.
- This definition is not intended to include experiences of relatively minor medical significance such as uncomplicated headache, nausea, vomiting, diarrhea, influenza, and accidental trauma (eg, sprained ankle) which may interfere with or prevent everyday life functions but do not constitute a substantial disruption.

Is a congenital anomaly/birth defect**Other situations:**

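### The mandatory nausea stop in Protocol 7.1.1 is tied to outpatient IV hydration, so read literally it misses direct admission with IV fluids given only as an inpatient

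*Protocol*

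**What the plan says.** Protocol Section 7.1.1 lists three individual stopping criteria, any one of which makes permanent discontinuation mandatory. The nausea criterion is "Nausea that prevents daily activity, requires outpatient IV hydration, and is assessed by the Investigator as a related AE". The dizziness criterion beside it has the same three-part form but asks only for a medical intervention, with no care setting named.

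Outside the stopping rules, three other provisions could lead to a change in dosing:

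- Section 7.1 gives a permissive list under the words "A subject may discontinue IP or withdraw from the study for the following reasons"; it includes adverse event and physician decision.
- Section 8 says immediate safety concerns should be discussed at once with the Medical Monitor "to determine if the subject should continue or discontinue IP".
- Section 6.5.1 allows dose reduction for treatment-related adverse events: "Dose modification of IP may be undertaken only after consultation and approval from the" Medical Monitor or designee. It also allows a later return to a higher dose in consultation.

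Nausea is one of the two potential risks named in Section 2.3.2: "The overall incidence of nausea was 18.8% (22/117) in GB004-treated subjects versus none in placebo-treated subjects".

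**The concern.** A mandatory stop exists to take a class of cases out of case-by-case judgement, and it should bind more firmly as cases get worse. As worded, this one does the reverse at one point. Outpatient fluids force a permanent stop. Direct admission with fluids given only as an inpatient meets the first and third conditions but not the second, so no stop is required. For the admitted subject, reducing the dose and later raising it again under Section 6.5.1 could comply with the protocol; for the subject treated as an outpatient it could not.

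The boundary is also blurred. Appendix 3 describes hospitalization as being detained "at the hospital or emergency ward for observation and/or treatment", usually at least overnight. IV fluids during an overnight emergency-ward stay could therefore be classed either way, and the mandatory stop would turn on that label.

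What is at stake is subject safety and consistent application across sites, not the efficacy analysis.

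**Working it through.** The plan gives no figure on this point. The check is a reading of the rule against the rest of the protocol, followed by a rough bound on how often it could matter.

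**1. Does another mandatory rule catch the case?**

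- Section 7.1.1, other items: a hemoglobin rise, and dizziness. Neither applies to nausea alone.
- Section 7.1.2: QTcF above 500 msec. Does not apply.
- Section 7.1.3 and Appendix 7, Table 7: nausea is named as a symptom, but only together with ALT or AST at least 3 × ULN. Nausea with normal liver tests is not covered.
- Sections 7.1.4 and 7.1.5: pregnancy, and new UC therapy. Do not apply.
- Appendix 3: admission makes the event an SAE. That triggers reporting; the definition does not require a stop.
- The SAP has no rule on this point.

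No mandatory rule catches the case. The routes in Sections 7.1, 8 and 6.5.1 permit a stop or direct a discussion; none fixes the outcome.

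**2. Literal outcome by care setting**, for nausea that is related and prevents daily activity:

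| Case | As written | *Outpatient* deleted |
|---|---|---|
| 1. Outpatient IV fluids only | stop | stop |
| 2. Outpatient IV fluids, then admission | stop | stop |
| 3. Direct admission, inpatient IV fluids only | **no stop** | **stop** |
| 4. Admission, no IV fluids | no stop | no stop |
| 5. No IV fluids, no admission | no stop | no stop |

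Deleting the word changes case 3 alone. Adding a separate hospitalization trigger would change cases 3 and 4. The table shows the scope of the wording; the rows are not equally likely.

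**3. How often could it matter?** Inputs from Section 2.3.2: 117 subjects treated with GB004, 22 with nausea, 1 discontinuation; 23 treated subjects with UC, nausea in 21.7%. Input from Section 9.2.1: about 65 per group, hence 2 × 65 = 130 on GB004 in the placebo-controlled period.

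- Nausea overall: 22/117 = 18.8%, matching the protocol.
- Nausea in the UC study: 5/23 = 21.7%, matching the protocol.
- Discontinued, among those with nausea: 1/22 = 4.5%.
- Discontinued for nausea, among all treated: 1/117 = 0.85%, Clopper-Pearson 95% CI 0.02% to 4.67%.
- Carried over to this trial: 130 × 0.0085 = 1.1 subjects; limits 130 × 0.0002 = 0.03 and 130 × 0.0467 = 6.1.

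This covers nausea discontinuations in every setting. The direct-admission case would be some unknown and probably small part of it. The protocol reports no admission for nausea.

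**4. How far does the earlier experience carry over?** Earlier doses reached 240 mg daily, and the longest dosing was 28 days (at 120 mg daily). The higher arm here takes 2 × 480 = 960 mg daily, and 960/240 = 4 times that maximum, for up to 36 weeks before the extension. Nausea was more frequent at 120 mg or greater. In the other direction, the formulation study that included the tablets had nausea in 9%, tablets gave less nausea than solution in preliminary data, and dosing here is with food.

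**The case against.** The strongest reply is that *outpatient IV hydration* is plainly a floor. The hemoglobin and QTcF criteria are floors that worse cases exceed, and most investigators would treat an admission for IV fluids as exceeding this one. That is probably the intent. It does not settle the matter, because those neighbouring floors are written as inequalities while this one names a setting with no *at least*, and Section 8 allows no waivers.

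Second, the missed case is narrow: any outpatient fluids before admission already trigger the stop. This is correct and limits the weight.

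Third, the safeguards are real. For an acute admission the discussion with the Medical Monitor is the directed procedure, not merely one option among several. SAE reporting runs within 24 hours, the investigator can stop product for an adverse event or by physician decision, and the DRC sees unblinded safety data. All of this stands, and it is why practical risk is low. But each safeguard leads to a decision, where the outpatient case has a fixed outcome.

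Fourth, nausea does feature in another mandatory action, the Table 7 interruption. That is so, but only with raised transaminases.

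Fifth, the projection measures all nausea discontinuations, not the case at issue. That is true; it serves only as a rough guide.

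Last, the proposed wording still leaves admission without IV fluids to judgement. That is deliberate: the criterion takes IV hydration as its mark of severity, and Appendix 3 counts stays for observation as hospitalization.

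**Conclusion.** The concern holds as a minor defect of wording in a safety rule. Taken literally, the only mandatory stop for nausea without raised transaminases binds the milder care setting and omits direct admission with inpatient-only IV fluids. One of the five care-setting cases is affected.

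The frequency of that case cannot be estimated from the documents. The nearest guide is about 1 nausea discontinuation of any kind (range 0 to 6) among some 130 GB004 subjects. It assumes that the earlier rate of 1/117 carries over despite higher doses and longer exposure.

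The conclusion rests on the literal text. It does not claim that such a subject would in practice be kept on product. No effect on the primary endpoint, power or analyses is claimed.

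**What to change.** In Protocol Section 7.1.1, delete *outpatient* from the nausea criterion, or state that IV hydration counts whether given as an outpatient or an inpatient. Do not add a separate hospitalization trigger, since that would also force a stop for admissions without IV fluids, including stays for observation only. The dizziness criterion shows that the rule works without naming a setting.

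The cost is one word at the next amendment. Sample size, visits and the SAP are unaffected.
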